12. ETHICAL CONSIDERATIONS

12.1 Regulation statement

This study will be conducted according to the principles of the Declaration of Helsinki (64th WMA General Assembly, Fortaleza, Brazil, October 2013; version 2013; www.wma.net) and in accordance with the Medical Research Involving Human Subjects Act (WMO).

12.2 Recruitment and consent

The investigator will identify potential subjects according to the aforementioned criteria.

Eligible patients are informed about the study and are asked for their participation.

Enrolment will take place in two ways;

- First directly via the LUMC, the LUMC is national referral center for intrauterine therapy. Parents of children that survived FNAIT will be invited to participate by sending a patient information letter and information leaflet for children. In this way, the parents will be informed that they will be contacted by phone approximately two weeks after sending the information letter.
- Secondly patients will be asked via Stichting Sanquin Bloedvoorziening, Sanquin is the national reference laboratory to diagnose FNAIT. Retrospectively all FNAIT cases are collected in the Laboratory of platelet and leukocyte serology of Sanquin. Referring specialists (mostly pediatricians) will be asked to obtain permission from the parents to inform them about our study by letter enclosed by the patient information leaflet. If parents do not object to be informed they will be contacted by our research team approximately two weeks after sending this letter.

When parents wish not to be approached by our research team they can indicate this by responding by e-mail, phone or reply letter. Informed consent is obtained from all patients who are willing to participate. In case of minors both parents or their guardian will be asked for participation and informed consent. The patient information letter and informed consent form will be attached as a separate document. If informed consent is given, assessment will be planned. At most, 3 attempts will be made to contact parents by phone. It is expected that enrollment for this study will cover a period of one year.

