2. INTRODUCTION AND RATIONALE

Fetal and neonatal alloimmune thrombocytopenia (FNAIT) is the most common cause of thrombocytopenia in otherwise healthy term-born neonates. [1] FNAIT is a rare disease with an incidence estimated around 1 per 1000 live newborns. [2] During pregnancy alloimmunization can occur due to incompatibility of the Human Platelet Antigens (HPA) on the maternal and fetal platelets. Alloimmunization and maternal production of antibodies directed against the HPA-positive fetal platelets, leads to thrombocytopenia and an increased risk of intracranial hemorrhages (ICH) in the fetus. Clinical presentation can vary from skin bleedings to severe ICH leading to lifelong neurologic sequelae or intrauterine death. [2] [3]

In the past, FNAIT was managed with invasive and high-risk interventions including intrauterine platelet transfusion (IUPT). Since the end of the 20th century, invasive intrauterine transfusions (IUT) were replaced by a new, non-invasive therapy: maternal administration of intravenous immunoglobulin (IVIg). This novel therapy resulted in a significant lower risk of intrauterine fetal death and ICH. [4] Intervention with immune modulation in the semi -allogenic environment of the fetus by administration of immunoglobulins (Ig) is successful, especially in preventing ICH. [5] However antenatal treatment with IVIg has been implemented as standard of care without strong methodological follow-up research of children from mothers treated with IVIg. To date, only two follow-up studies have been published in children with anticipated FNAIT cases. The first study of a FNAIT cohort treated with IVIg was done by Ward et al. in 2006. [6] They concluded that development of children treated for FNAIT was better compared to their non-treated siblings. Their conclusions were based on non-validated questionnaires taken by telephone, assessing the behavioral outcome of the children and were limited by a ~40% lost-to-follow-up rate. [6] A second follow-up study including 39 children was published by a research group from our center in 2004. This research stated that the outcome in children with FNAIT and exposed to maternal IVIg treatment was similar to the normal population. However, this study included a heterogenic group of children with different treatment strategies including IUT, hampering definitive conclusions and substantiating the need for more research. [7]

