3.3 Other study parameters

We will gather the data about the following data of our cases; age and sex of the child, obstetric medical data and neonatal characteristics and morbidity of the study population. Parents will be asked to complete a questionnaire to assess the highest level of education of the parents. We use this data to describe our study population and correct for potential confounding of these factors on neurodevelopmental outcome as described in chapter 11. Study parameters are summarized in Table 1, a list of definitions can be found in Table 3.

Possible confounding factors for allergies are the family history for asthma, allergies or eczema. For evaluation of the infections it is important to assess smoking at home and day-care visit as possible confounding factors.

Table 1: Study parameters

Study parameters		
Obstetric data	Maternal characteristics	Age mother at delivery Obstetric history Medication usage during pregnancy
	Pregnancy characteristics	Gravidity/Parity Pregnancy induced hypertension Pre-eclampsia Signs of bleeding in the fetus at ultrasound
	FNAIT related therapy	IVIg treatment Intra-uterine transfusions Treatment with corticosteroids
	Labour characteristics	Mode parturition Gestational age at delivery
	Placental features	Placenta weight
Neonatal data	Birth data	Gestational age at birth Birthweight Apgar score
	Severe neonatal morbidity	Respiratory distress syndrome Perinatal asphyxia Proven early onset neonatal sepsis Retinopathy of prematurity Necrotizing enterocolitis
	Neonatal neurologic sequelae	Intracranial haemorrhage Cystic periventricular leukomalacia Ventricular dilatation Porencephalic or parenchymal cysts Convulsions Any cerebral lesions associated with adverse neurologic outcome
	Signs of bleeding	Skin manifestations Intracerebral bleeding Organ bleeding Increased bleeding tendency, reported by the caregiver
	Therapy	Platelet transfusions IVIg treatment

Table 1: Study parameters

[figure not shown]
Study parameters		
Laboratory data	HPA	HPA incompatibility HPA genotyping Anti-HPA-titre Platelet count Directly after birth Nadir Other Presence of HLA class I antibodies

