5.4 Sample size calculation

Of note, performing sample size calculations in the context of this rare disease is difficult since literature is scarce and heterogeneous.

We performed two different sample size calculations for the two cohorts.

Cohort 1: Using the literature to date we estimated that the IQ score of FNAIT survivors without antenatal treatment is lower, that is 92 versus average (100) in the normal population. To show a difference in IQ score between FNAIT survivors without IVIg treatment compared to a fixed average of 100, we performed a sample size calculation for a one-sample t-test. We calculated that a minimum group size of 39 was needed to show a mean difference of 7 IQ points with a power of 0.8 and a significance of 0.05. We assume a standard deviation (SD) of 15 for the IQ score.

Cohort 2: In the FNAIT survivors with antenatal treatment we expect no difference in IQ score between cases and the national average. To show that there is no difference IQ score in anticipated IVIg treatment compared to the Dutch average we perform a non-inferiority calculation by a one-sample t-test. In this case we need a sample size of 39 children with a non-inferiority margin of 7 IQ points, with a power of 0.8 and a significance level of 0.025. We assume a standard deviation (SD) of 15 for the IQ score.

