11. STATISTICAL ANALYSIS

Continuous parametric data will be presented with mean \pm standard deviation (SD) or median with interquartile range (IQR) as appropriate. Categorical data will be presented as counts and percentages within each study group.

The cognitive test score of both cohorts will be compared with the Dutch average by using a linear regression model. The following potential confounders for cognitive development (IQ score) identified in earlier research will be used in the analysis;

- Sex
- Gestational age at birth
- Small for gestational age
- Neonatal morbidity
- Level of education of the parents

In second cohort; the FNAIT survivors with IVIg treatment atopic constitution and the course of infections will be assessed in a secondary analysis.

In the assessment of course of infections the following confounders will be used in the analysis by using a linear regression model;

- Day-care visit
- Smoking in a household
- Time of the year that the questionnaire was filled in

In the analysis of allergies and asthma the following confounders will be used in the analysis by using a linear regression model;

- Presence of a first degree family member with asthma eczema or allergy
- Smoking in a household

All data is analysed with IBM SPSS Statistics version 24 (IBM Software, NY, USA, 2016).

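### Each volunteer cohort is compared with a fixed norm of 100, with no reference distribution for parental education and no bound on selective participation

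*Combined protocol and SAP*

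**What the plan says.** The comparator is a constant. Section 5.4 sizes cohort 1 "compared to a fixed average of 100, we performed a sample size calculation for a one-sample t-test", and cohort 2 as a one-sample non-inferiority test with a 7-point margin. Section 11 says: "The cognitive test score of both cohorts will be compared with the Dutch average by using a linear regression model". It names no comparator data set.

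Section 11 lists "Level of education of the parents" among the covariates. Section 3.3 explains the source and purpose: "Parents will be asked to complete a questionnaire to assess the highest level of education of the parents", and "We use this data to describe our study population and correct for potential confounding of these factors on neurodevelopmental outcome as described in chapter 11". No national education distribution, centring value or weighting scheme is given.

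Section 3.1 aims at all FNAIT survivors in each cohort. Under section 12.2 there are two routes of invitation. On the laboratory route, "Referring specialists (mostly pediatricians) will be asked to obtain permission from the parents to inform them about our study". Parents can decline to be approached, and "At most, 3 attempts will be made to contact parents by phone". Only families who consent are assessed. The documents give no expected participation rate, no comparison of participants with non-participants, and no sensitivity analysis for non-participation. Section 2 says that the conclusions of an earlier follow-up study "were limited by a ~40% lost-to-follow-up rate".

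**The concern.** A whole-population norm includes families of every kind. The study sample includes only those who agree. If agreement is related to parental education or to the child's development, the sample mean differs from the mean of all eligible survivors, and the comparison with 100 carries that difference.

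The education covariate looks like a remedy but is not one as specified. In a model fitted to the cohort alone, the adjusted difference from 100 is the intercept, and its value depends on where education is centred. The plan does not say where.

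Both primary conclusions are exposed. An upward shift hides a deficit in cohort 1 and favours non-inferiority in cohort 2. A downward shift creates a deficit in cohort 1 and makes non-inferiority harder to show in cohort 2.

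**Working it through.** **Inputs from section 5.4.** n = 39 per cohort, SD 15, power 0.8. Cohort 1: difference 7, significance level 0.05 (sidedness not stated). Cohort 2: margin 7, significance level 0.025. Participation rates, IQ gaps and education shares are not in the documents. Those below are assumptions.

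**The plan's own figure.** A one-sample t-test with the noncentral t distribution gives n = 39 for cohort 1 (two-sided 0.05) and n = 39 for cohort 2 (one-sided 0.025, true difference 0). Power at 39 is 0.811 in both. The sample size reproduces and is not in dispute.

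**Education covariate.** Assume 30% highly educated parents in the norm, 50% in the sample, a 10-point IQ gap between education groups and a true deficit of 7.
- Norm means: 100 − 0.3 × 10 = 97 (lower education) and 107 (higher).
- Cohort means with the deficit: 90 and 100. Sample mean: 0.5 × 90 + 0.5 × 100 = 95.
- Adjusted difference from 100: −10 with lower education as reference, 0 with higher education as reference, −5 centred on the sample.
- Centred on the norm: 0.7 × 90 + 0.3 × 100 − 100 = −7. Only this choice recovers the true deficit.

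The shift from education alone is (excess share of highly educated parents) × (IQ gap). For excess shares of 0.1 to 0.3 and gaps of 5 to 15 points, it runs from 0.1 × 5 = 0.5 to 0.3 × 15 = 4.5 points.

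**Non-participation.** Shift in the mean = (1 − participation rate) × (participant mean − non-participant mean).

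| Participation (assumed) | Gap 5 | Gap 7.5 | Gap 10 |
|---|---|---|---|
| 80% | 1.0 | 1.5 | 2.0 |
| 60% | 2.0 | 3.0 | 4.0 |
| 50% | 2.5 | 3.75 | 5.0 |

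**Effect on the tests.** The noncentrality is (distance from the tested value, including the shift) × √39 / 15, with 38 degrees of freedom. Cohort 2 is tested against 100 − 7 = 93.

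| Upward shift | False non-inferiority, cohort 2 (true mean 93) | Power, cohort 1 (true deficit 7) |
|---|---|---|
| 0 | 2.5% | 81% |
| 1 | 6.0% | 68% |
| 2 | 12.5% | 53% |
| 3 | 22.9% | 37% |
| 4 | 36.8% | 23% |

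A downward shift follows by symmetry. At 2 points, with a true mean of 100, the chance of a false cohort 1 deficit rises from 2.5% (the lower tail of the two-sided 5% test) to 12.5%. Cohort 2 power falls from 81% to 53%, because the effective distance from the bound is 7 − 2 = 5.

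**Example of a tipping point.** The 95% half-width at n = 39 is 4.862. Suppose an observed cohort 2 mean of 100 and 60% participation, and hold the half-width fixed. The lower limit clears the bound by 100 − 4.862 − 93 = 2.138. Non-inferiority then reverses if non-participants average 2.138 / 0.4 = 5.3 points below participants, that is, about 94.7.

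**The case against.** Much of the case on the other side stands, and it limits the point.

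- *Direction.* A reader might infer that participation bias flatters the results. The documents do not support that. Section 12.4 promises families a report and, where needed, advice on support, which could attract worried families. It also says that most of the assessment is already routine for children treated with fetal therapy or with severe neonatal brain injury, who may be easier to reach.
- *Education.* A reader might infer that the plan ignores parental education. It does not: education is collected, classified and pre-specified as a covariate. If it were centred on the national distribution, the planned regression would give the standardised answer. What is missing is the reference distribution.
- *Awareness of bias.* Section 5.1 gives survival and recall bias as examples, so it cannot be read as a closed list that rules out participation bias. It offers no analysis for any of them.
- *Recruitment rules.* The three-call limit is ordinary conduct and nothing here asks to change it. The extra specialist step on the laboratory route could select families differently, but the documents do not show that it does.
- *Size.* Every participation and gap figure is assumed. The 37% figure combines 60% participation, a 10-point gap and a true mean exactly on the margin. At 80% participation and a 5-point gap, the figure is 6.0%.

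None of this supplies the missing reference distribution or a bound on non-participation.

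**Conclusion.** The point holds in a limited, direction-neutral form. As written, section 11 compares volunteers with a fixed 100, and the listed education covariate leaves the adjusted difference undefined until a reference distribution is stated. Nothing lets a reader judge how far selective participation could move either primary conclusion.

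The possible size is material for this design. Shifts of 1 to 4 points compare with a 7-point margin and a half-width of about 4.9, and they change the error rates as tabulated. These are illustrations on assumed inputs at SD 15 and n = 39, not estimates of the bias in this study. The sample size calculation is unaffected, and the documents do not show that the results will be biased. Label: cheap improvement.

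**What to change.** Add two items to section 11.

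1. As a pre-specified sensitivity analysis, standardise each cohort's mean IQ to the Dutch distribution of parental education, either by weighting or by centring the covariate on that distribution. Name the source in advance. Use two or three ISCED levels, because finer cells would be sparse with about 39 children.
2. Record invited and assessed numbers per cohort and route. From them, report the non-participant mean at which each primary conclusion would reverse, in either direction. On the laboratory route, count from the approach to the specialist, so that refusals at that step stay in the denominator. This needs counts only, with no data from families who decline.

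The first item deals only with measured education. The second covers selection for any reason and assumes no direction. The cost is a few lines in section 11, a recruitment log, a published national education distribution (which the documents do not contain) and a somewhat wider interval after standardising. The primary analysis and recruitment procedures can stay as they are.

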12.3 Objection by minors or incapacitated subjects

Neuropediatric examination and neurodevelopmental tests are performed by trained personnel who are in close contact with the child and parents to detect any resistance. All tests have age related items and can be performed in a playful way to avoid stress.

The investigators will follow the guidelines of the Dutch pediatric society concerning resistance or anxiety in minors during investigation procedures and the CCMO code of conduct concerning research with minors.

12.4 Benefits and risks assessment, group relatedness

Participation in the study does not result in individual benefits. There is no risk associated with study participation.

Our department has extensive experience in conducting neurodevelopmental assessment of children. The main part of the neurodevelopmental assessment and the completion of questionnaires are part of routine care for preterm children born with a gestational age <30 weeks and/or birth weight <1000 grams or <P10, for children treated with fetal therapy for children with documented severe neonatal brain injury. The examinations are performed according to the guidelines of the Dutch Neonatal follow-up (LNF) Study Group. Parents and children will receive a report of the test results and, if necessary, advice for further support and interventions.

12.5 Compensation for injury

A dispensation for the liability insurance was accredited by the METC Leiden Den Haag Delft.

12.6 Incentives

Children will receive a small present (to be determined, for example a stuffed animal) after the follow-up assessments. Parents receive a parking fee and travel allowance.

13. ADMINISTRATIVE ASPECTS, MONITORING AND PUBLICATION

13.1 Handling and storage of data and documents

Data management will be implemented according to Good Clinical Practice (GCP)-guidelines. Patient data will be entered by way of an eCRF in a central GCP proof internet-based database to facilitate on-site data-entry. Castor was chosen as our data management system. Data will be stored at the LUMC network. Security is guaranteed with login names, login codes and encrypted data transfer. The researchers will maintain the database and check the information in the database for completeness, consistency and plausibility with consultancy of the department advanced data management.

The data of all subjects will be coded and this coding will not be retraceable to the individual patient. The key to this coding is safeguarded by the investigator. A limited number of people have access to the source data. These are the principal investigators, investigating personnel. Personal data are only processed by the researchers or by those who fall directly under their authority. In addition, the study monitor, quality assurance auditor, employees from the Health Care Inspectorate of the Ministry of Health, welfare and Sport (Nederlandse Inspectie voor de Gezondheidszorg) have access to the source data. All are subject to the pledge of confidentiality. Data will be stored for 15 years strictly confidential.

Consent for our study or storage of personal data can be withdrawn at any time during our study. Research data that was collected till withdraw of permission will be used in our current study. The board of directors of the LUMC is responsible for processing data. The data protection officer, *functionaris gegevensbescherming*, of the LUMC or/and Sanquin can be contacted by participants when they have questions about the protection of their privacy.

13.2 Monitoring and Quality Assurance

The study will be monitored by the internal monitoring pool of the LUMC throughout its duration by means of personal visits to the investigator's facilities and through other communications (e.g., telephone calls, written correspondence). Monitoring visits will be scheduled, conform to the risk classification, once throughout the study and at frequency deemed appropriate for the study. For details we refer to the monitoring plan of the study.

This visit will be conducted to evaluate the progress of the study, ensure the rights and wellbeing of the subjects are protected, check that the reported clinical study data are

accurate, complete and verifiable from source documents, and the conduct of the study is in compliance with the approved protocol and amendments, GCP and applicable national regulatory requirements. A monitoring visit will include a review of the essential clinical study documents (regulatory documents, CRFs, source documents, subject informed consent forms, etc.) as well as discussion on the conduct of the study with the Investigator and staff. The Investigator and staff should be available during these visits to facilitate the review of the clinical study records and resolve/document any discrepancies found during the visit.

13.3 Amendments

Amendments are changes made to the research after a favourable opinion by the accredited METC has been given. All amendments will be notified to the METC that gave a favourable opinion.

13.4 Annual progress report

The sponsor/investigator will submit a summary of the progress of the trial to the accredited METC once a year. Information will be provided on the date of inclusion of the first subject, numbers of subjects included and numbers of subjects that have completed the trial, serious adverse events/ serious adverse reactions, other problems, and amendments.

13.5 Temporary halt and (prematurely) end of study report

The investigator/sponsor will notify the accredited METC of the end of the study within a period of 8 weeks. The end of the study is defined as the last patient's last visit.

The sponsor will notify the METC immediately of a temporary halt of the study, including the reason of such an action. In case the study is ended prematurely, the sponsor will notify the accredited METC within 15 days, including the reasons for the premature termination.

Within one year after the end of the study, the investigator/sponsor will submit a final study report with the results of the study, including any publications/abstracts of the study, to the accredited METC.

In case the final study report will not be available within one year, another term should be defined including the reasons.

